12.6.2.1 Main Analysis

Missing Data Strategy

The outcome data that will be missing or set to missing following an intercurrent event, will be assumed to be missing at random (MAR) and will be handled through model-based restricted maximum likelihood (REML) estimates.

Statistical Model

A mixed model analysis of variance (ANOVA) will be conducted on AUCs, and C_{max} endpoints in the natural logarithmic scale.

The model will include terms for sequence, period, product exposure as fixed effects and subject as a categorical random effect modeling the within subject correlations.

An heterogeneous Compound Symmetry matrix will be used to model the variancecovariance structure within subjects. If this model fails to converge, then the following variance-covariance matrix will be used (in this order) until one converges. Variance Components, Compound Symmetry, and finally no repeated statement.

Confidentiality Statement

Philip Morris Products S.A.	Clinical Study Protocol	Confidential
P5-PK-01-EXP	2.0, Approved	Page 82 of 98
Related to QMS-0017588		Document ID: VV-TMF-00821

The procedure will use the restricted maximum likelihood method and the Kenward-Roger method to compute the degrees of freedom.

The results of this analysis will be presented in terms of geometric least square mean ratios and 95% confidence intervals (95% CI) for the 4 respective variants of NP 1.0, Velo-NP and Zyn-NP ratios. The pairwise comparisons which will be performed are listed in Table 10.

	NP-2	NP-3	NP-4	Velo-NP	Zyn-NP
NP-1	X	X	x	X	X
NP-2		x	x	X	x
NP-3			x	x	x
NP-4				x	x

Table 10 List of pairwise comparisons

The model described above will be implemented in the SAS® language as:

```
PROC MIXED data=dataset method=reml;
    class Subject Sequence Period Product Sex;
    model Log(Parameter) = Sequence Period Product / ddfm=KR;
    repeated Product / subject=Subject type=csh;
    lsmeans Product / pdiff=LIST_OF_PAIRWISE_COMPARISONS cl;
PUN.
```

RUN;

The analysis of T_{max} will be performed by conducting a Wilcoxon signed rank test and calculating the median T_{max} for each product along with the Hodges-Lehmann estimate of the median difference between products, and the related 95% CI.

12.6.2.2 Sensitivity Analysis

In case the plasma concentrations cannot be background-corrected in 2 or more subjects in a sequence a sensitivity analysis will be performed similarly to the main analysis, whereby:

- If the subject's terminal elimination rate cannot be estimated it will be substituted by the average terminal elimination rate of the subjects having the same sex,
- If the uncorrected nicotine concentration at baseline is not available for the period 2 or 3, it will be substituted by the extrapolation of the previous concentrations using the terminal elimination rate.

Confidentiality Statement

12.6.2.3 Supplementary Analysis

In case of any uncorrected nicotine concentration at T_0 [uC₀] greater than 25% of their uncorrected maximum value, a supplementary analysis of the endpoints will be performed similarly to the main analysis, whereby data of these subjects for this specific study day will be excluded from the analysis.

An analysis of covariance (ANCOVA) will be conducted by product use. The PK parameters will be transformed in the natural logarithmic scale. The model will include terms for sequence, period and a PD parameters mentioned in the objective 4. The results of this analysis will be presented by product in terms of:

- The percentage of variance explained by the PD parameter
- The standardized effect of the PD parameter, defined as the mean effect divided by the square root of its variance.

Another analysis of covariance (ANCOVA) will be conducted similarly at the exception that it will be performed overall using mixed effects ANCOVA where the model will include additionally the subject as a categorical random effect to model the within subject correlations.

A multivariate analysis will be performed to analyze the joint effect of nicotine concentration, PH and moisture. The PK parameters will be transformed in the natural logarithmic scale. The model will include be adjusted for product use, sequence, period, and covariates encoded as low and high for nicotine concentration, PH level and moisture percentage. The results of this analysis will be presented for all products. The output will contain regression coefficients and their confidence intervals for factors of interests. Further details will be provided in the SAP.

12.7 Safety Analysis

In general, all safety data will be listed and tabulated in the Safety population using the approach described in section 12.1.3. Safety variables collected during exposure period will also be reported by sequence.

AE data will serve for the assessment of safety. Other safety variables monitored in this study include: incidence of NP 1.0 product events including malfunction/misuse; vital signs (systolic and diastolic blood pressure, pulse rate, respiratory rate); ECG data; clinical chemistry, hematology, and urine analysis safety panel; concomitant medication.

The number and percentage of subjects with AEs, SAEs, and product events will be tabulated by system organ class and preferred term. Summaries will also be presented for AEs leading to product discontinuation, AEs leading to study discontinuation, AEs by relatedness to product exposure (including expectedness) and relatedness to study procedures, AEs by severity, and AE by action taken related to the product. Tabulations will include the number of subjects experiencing an event and the number of events.

Confidentiality Statement

Philip Morris Products S.A.	Clinical Study Protocol	Confidential
P5-PK-01-EXP	2.0, Approved	Page 84 of 98

Safety laboratory assessments are performed on Day -1 and Day 3 in the morning prior to product use (). Any lab related AEs on Day 3 will be assigned to the product used on the previous day.

Summary tables showing actual values and change from baseline of clinical findings will be provided for ECGs, vital signs, and laboratory parameter. Descriptive statistics will be summarized by period for ECG and vital signs and by Day for laboratory parameters, ECG and vital signs.

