4 INVESTIGATIONAL PLAN

4.1 Overall Study Design and Plan

This is a single-center, randomized, controlled, open-label, cross-over study in healthy subjects to investigate the nicotine pharmacokinetic profiles of four variants of Nicotine pouch 1.0, compared to Velo-NP and Zyn-NP. In addition, PD effects (subjective effects and related behavioral assessments) will be evaluated to provide further insights on Nicotine pouch 1.0 product acceptance and abuse liability. The study will be conducted with 3 periods and in a 6 sequence-cross-over design.

A Screening Visit will be conducted within 21 days (Day -22 to Day -2) prior to Admission (Day -1) to the investigational site (Figure 2).

A sufficient number of subjects will be screened to ensure that 24 subjects will be randomized into the study with at least 25% of each sex.

Confidentiality Statement

Philip Morris Products S.A.	Clinical Study Protocol	Confidential
P5-PK-01-EXP	2.0, Approved	Page 33 of 98

Qualified subjects will return to the investigational site for Day -1. Subjects should have fasted for at least 10 hours prior to the safety laboratory assessments. After confirmation of eligibility, subjects will be enrolled. All subjects that are not enrolled will be considered as screen failures.

On Day -1, enrolled subjects will perform a product test using NP-1 for 30 minutes (± 1 minute). After the product test, subjects not willing and/or not ready to use Nicotine pouch 1.0 during the study will be discontinued from the study, will enter the 3-day Safety follow-up period and will be replaced.

Subjects willing and ready to use 4 variants of Nicotine pouch 1.0, Velo-NP and Zyn-NP during the study after product test will start their confinement period of 3 days.

24 subjects will be randomized to 1 of 6 possible sequences of product use on Day 1 to Day 3 with at least 25% of each sex.

On Day 1 to Day 3, after at least 8 hours of abstinence from any nicotine/tobacco containing products (nicotine wash-out), subjects will use one variant of Nicotine pouch 1.0, Velo-NP or Zyn-NP according to randomized product use sequence for 30 minutes (\pm 1 minute). The used nicotine pouches will be collected for long-term storage to determine the residual nicotine after product use to estimate the amount of nicotine delivered during the 30 minutes use period.

Subjects will complete questionnaires about product evaluation, craving and liking assessments.

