6.2.2 Exposure Period (Day 1 to Day 3)

After at least 8 hours of abstinence from any nicotine/tobacco containing products (nicotine wash-out), subjects will use one NP according to randomized product use sequence for 30 minutes (± 1 minute) in the morning and in the afternoon. One nicotine pouch will be placed between the upper lip and the gum for 30 minutes and subjects will be instructed not to manipulate the pouch with the tongue or lips. The same application site should be used for all products.

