T9 after 1 hour ± 5		Product evaluation scale	Section 7.8.3
minutes		Sensory questionnaire	Section 7.8.8
Within 15 minutes prior to T_{0A}		VAS craving	Section 7.8.4
T-1 5 minutes \pm 1 minute prior to T _{0A}	Х	Blood sampling for baseline nicotine level	Section 7.5.1
Just before T_{0A}		Providing 1 NP 1.0 or Velo-NP or Zyn-NP	Performed by investigational site staff
Start of product use: T _{0A}		Placing NP 1.0 or Velo-NP or Zyn- NP between the upper lip and gum	Section 6.2.2
T1 after 5 ± 1 minutes T2 after 10 ± 1 minutes T3 after 15 ± 1 minutes T4 after 20 ± 1 minutes T5 after 25 ± 1 minutes T6 after 30 ± 1 minutes T7 after 35 ± 1 minutes T8 after 40 ± 1 minutes T9 after 1 hour ± 5 minutes T10 after 3 hours ± 5 minutes T11 after 6 hours ± 5 minutes	X	Blood sampling for nicotine PK VAS craving, VAS liking (in the moment) and VAS satisfaction	Section 7.5.1 Section 7.8.4 Section 7.8.5 Section 7.8.6 VAS craving and VAS satisfaction only VAS craving and VAS satisfaction only
After 30 minutes of product use T9 after 1 hour ± 5 minutes Between 2 hours after T _{0A} and Discharge		Collection of used NP 1.0, Velo-NP or Zyn-NP Product evaluation scale Sensory questionnaire Collection of spot urine for: • Urine analysis safety panel • Urine pregnancy test (all female subjects)	Section 7.8.3 Section 7.8.8 Section 7.6.1 Section 7.6.5

Confidentiality Statement

Confidential Page 71 of 98

Related to QMS-0017588

Document ID: VV-TMF-00821

Time	Blood Sample	Procedures	Additional Information
		Concomitant medication/concomitant disease status	
		Physical examination	Section 7.4.3
		ECG	Section 7.4.7
During the visit		Information on the risk of smoking/advice on smoking cessation and debriefing on Nicotine pouch 1.0	Section 7.2
During the visit		AE/SAE recording	Section 8.2
		Product events	Section 8.7
		Discharge	

Abbreviations: AE = Adverse event; ECG = Electrocardiogram; PK = Pharmacokinetic; SAE = Serious adverse event; VAS = Visual analogue scale

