12.9 Measures to Control Bias

12.9.1 Method for Assigning Subjects to Study sequences

The study will be conducted with 6-period and 6 sequences in a cross-over Williams design [37]. A Williams design is an orthogonal Latin squares design with balanced property [38]. On day -1, subjects will be randomized to one of the six study sequences. Details about the randomization process will be included in the Data Management Plan (DMP).

A minimum quota of each sex will be applied to ensure they represent at least 25% of the total study randomized population.

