a. Prior to enrollment at Admission on Day -1, the following inclusion and exclusion criteria will be re-checked: Inclusion Criteria: (4) Subject has smoked ≥ 10 commercially available cigarettes per day for 4 weeks prior to Screening Visit and Admission. Smoking status will be verified based on a urinary cotinine test (cotinine ≥ 500 ng/mL), (5) Subject does not plan to quit smoking or using other nicotine/tobacco-containing products in the next 3 months. Exclusion criteria: (10) Subject has a positive urine drug including alcohol test, (15) For women only: subject is pregnant (does not have negative pregnancy tests at Screening Visit and Admission) or is breastfeeding, (16) For women of childbearing potential only: subject does not agree to use an acceptable method of effective contraception, (17) Use of estrogen-containing hormonal contraception or hormone replacement therapy.

Confidentiality Statement

Philip Morris Products S.A.	Clinical Study Protocol	Confidential
P5-PK-01-EXP	2.0, Approved	Page 97 of 98

Document ID: VV-TMF-00821

The following eligibility criteria will only be checked at Admission: (7) Subject has received medication within 14 days or within 5 half-lives of the drug prior to Admission, whichever is longer, which has an impact on CYP2A6 activity.

- b. Sex, date of birth/age, race and ethnicity.
- c. Concomitant disease status.
- d. All medication taken within 4 weeks prior to the Screening Visit will be documented. Prior medication which has an impact on CYP2A6 activity taken within 14 days or within 5 half-lives of the drug (whichever is longer) prior to Day -1 is an exclusion criterion.
- e. Systolic and diastolic blood pressure, pulse rate and respiratory rate. On Day 1 to Day 3 in the morning, vital signs will be assessed prior to T_{0M} .
- f. At Screening an ECG will be performed after signed ICF and at least 1 hour after smoking cigarettes, on Day -1 an ECG will be performed prior to enrollment, on Day 3 an ECG will be performed 60 minutes \pm 10 minutes after T₀.
- g. Blood samples should be taken in the morning of the Screening visit, Admission (Day -1) and Discharge (Day 3) or at Early termination. Subjects should have fasted for at least 10 hours prior to safety laboratory assessments except at the Screening visit and Early termination where non-fasting samples will be used.

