8.6 Adverse Events

All AEs occurring during this clinical trial will be coded using MedDRA® using the version specified in the DMP.

All AEs captured in the database will be listed in by subject data listings including verbatim term, coded term, product, severity, relationship to study product, and action taken; All adverse events will be summarized. Adverse events that occur after ICF and prior to the product test on Day -1 and those that occur during the safety follow up (FU) period (after discharge to safety FU visit) will be summarized separately under admission/safety FU period.

A study product use-emergent adverse event is defined as an AE that is starting or worsening at the time of or after study product administration. An AE that occurs during the washout period between study products is considered study product use emergent to the last study product given.

If the onset time of an AE is missing and the onset date is the same as the product administration date, the AE will be considered product use-emergent to the prior and current product. If the onset time of an AE is missing and the onset date does not fall on a product administration date, the AE will be considered product use-emergent for the last product administered. If the onset date of an AE is missing, the AE will be considered product use-emergent and attributed to each product on the study, unless the onset date is known to have occurred within or between specific product periods.

All PUEAEs will be summarized by product and overall. The number and percentage of subjects with AEs, SAEs (including deaths), and product events listed will be tabulated by

Statistical Analysis Plan Number CA36095

system organ class and preferred term. Summaries will also be presented for AEs leading to product discontinuation, AEs leading to study discontinuation, AEs by relatedness to product exposure (including expectedness) and relatedness to study procedures, AEs by severity, and AE by action taken related to the product. Tabulations will be performed for both the number of subjects experiencing an event and the number of events.

SAEs, if present, will also be listed. Applicable narratives will be included in the CSR.

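### The Protocol 12.7 rule for Day 3 laboratory AEs does not identify one product for blood, and for urine it conflicts with Table 8 and SAP 8.6

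*Protocol*

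**What the plan says.** Protocol 12.7 gives a sampling premise and then an attribution rule. The premise is "Safety laboratory assessments are performed on Day -1 and Day 3 in the morning prior to product use". The rule is "Any lab related AEs on Day 3 will be assigned to the product used on the previous day". Neither separates blood from urine, and 12.7 counts the urine panel among the safety variables.

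The exposure schedule has two uses a day. Protocol 6.2.2 says "subjects will use one NP according to randomized product use sequence for 30 minutes (± 1 minute) in the morning and in the afternoon", and 12.9.1 describes "6-period and 6 sequences in a cross-over Williams design". SAP 3.1 and 6.1 agree.

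On sampling times, note g of Protocol Appendix A says "Blood samples should be taken in the morning of the Screening visit, Admission (Day -1) and Discharge (Day 3) or at Early termination". Table 8 (Protocol 9.5) lists the Day 3 blood ahead of the procedures for the morning use. The same table has a later row, timed between 2 hours after the start of the afternoon use (T0A) and discharge, that reads "Collection of spot urine for: • Urine analysis safety panel".

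SAP 8.6 has its own attribution rule: "An AE that occurs during the washout period between study products is considered study product use emergent to the last study product given". Where no onset time is recorded and the onset date is a product-use date, it assigns the AE to both the preceding and the current product. The SAP neither repeats nor withdraws the 12.7 rule, and SAP section 9 declares no change on this point.

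**The concern.** The 12.7 rule reads as if each day had one product. With two, its singular product has two possible referents on Day 2. Its timing premise also fails for one of the two Day 3 sample types.

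Safety and tolerability is objective 3. Protocol 8.4 requires clinically significant abnormal test results to be reported as AEs, and SAP 8.6 tabulates product-use-emergent AEs by product. Any AE arising from a Day 3 laboratory result must therefore be placed in a product row. As the documents stand, whoever programs the tables has to choose between two rules, possibly after seeing the data.

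The SAP did change the unit elsewhere. The supplementary analysis in Protocol 12.6.2.3 excludes data by study day; SAP 6.5.3 excludes them by product use period. The laboratory AE rule received no such change.

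**Working it through.** **1. Confirm uses per day from the plan's own blood budget (Protocol 7.7.1).**
- Nicotine samples: 2 uses × 12 samples × 3 days + 2 extra on Day 2 = 74.
- Volume: 74 × 4.0 mL = 296 mL, the stated figure. One use a day would give (12 × 3 + 2) × 4.0 = 152 mL.
- Safety draws: 37.5 / 12.5 = 3, matching Screening, Day -1 and Day 3. There is no scheduled safety blood between Day -1 and Day 3.
- Total: 296 + 5 + 37.5 = 338.5 mL, against approximately 340 mL stated.

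**2. Map periods to days.** Periods 1 and 2 fall on Day 1, 3 and 4 on Day 2, 5 and 6 on Day 3. The Day -1 safety sample is taken before enrollment, and the NP-1 product test follows enrollment (Table 5).

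**3. Apply each rule to each Day 3 sample.** The onset of a laboratory AE is taken as the sample time, which is an assumption.

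| | Day 3 blood | Day 3 urine panel |
|---|---|---|
| Timing | morning, before use | between 2 h after T0A and discharge |
| Uses since the Day -1 sample | NP-1 test + periods 1–4 = 5 | NP-1 test + periods 1–6 = 7 |
| Fits the 12.7 premise? | yes | no |
| Protocol 12.7 | period 3 or period 4 | period 3 or period 4 |
| SAP 8.6, onset time known | period 4 | period 6 |
| SAP 8.6, onset time missing | preceding and current product; the current one is not yet used at the draw | preceding and current product; Day 3 has two uses |

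The period 6 entry extends the SAP sentence slightly. It is worded for gaps between products, and no product follows period 6.

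**4. Check agreement.** For blood with a known time, the SAP's answer is one of the two that 12.7 allows. For urine it is never one of them. Each product is used once, so the period 6 product cannot also be a period 3 or 4 product, whatever the sequence. Enumerating a balanced 6 × 6 Williams square gives 0 of 24 subjects in whom they coincide.

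**5. Who is in the Day 2 position.** Protocol 4.1 says "24 subjects will be randomized to 1 of 6 possible sequences of product use on Day 1 to Day 3". If the split is equal, 4 per sequence (not stated), each product is used on Day 2 by 2 × 4 = 8 of 24 subjects and is the last Day 2 product in 4 of 24. Under the 12.7 rule, a product's chance of being charged depends on its place in the sequence.

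**The case against.** The best reply is that SAP 8.6 already does the work. A Day 3 morning blood finding falls in a washout, the last product given is the Day 2 afternoon one, and that is a product of the previous day, so the two documents agree. For blood with a known onset time this stands. It does not cover a missing onset time, and it does not help with urine.

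A second reply is that the two sentences in 12.7 belong together, so urine taken after use falls outside the rule. That is a fair reading of intent. The wording, however, covers any Day 3 laboratory AE, and the protocol treats the urine panel as part of the safety laboratory (7.6.1).

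A reader might infer more than the documents support:

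- *That none of the Day 3 samples fits the rule, so the attribution is wrong throughout.* Haematology and chemistry do fit the premise: morning draw, 10-hour fast (Protocol 6.6.2 and 7.6.1), listed before the morning use. The rule is ambiguous for blood and contradicted for urine.
- *That a third of the laboratory safety evidence is missing.* Periods 5 and 6 are 48 of 24 × 6 = 144 planned uses (33%) and have no later scheduled blood sample. But Protocol 12.7 and SAP 8.7 summarise laboratory values by day. The 33% describes the coverage of a by-product laboratory summary that nobody plans, and it does not count misattributed AEs.
- *That the Day 3 blood draw should be moved.* That would collide with the morning and fasting requirements, and nothing here needs it.

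**Conclusion.** The point holds in a limited form. For Day 3 blood, 12.7 does not name one product; SAP 8.6 settles it when the onset time is known and not when it is missing. For Day 3 urine, the 12.7 premise contradicts Table 8, and 12.7 and SAP 8.6 give different products for the same event in every subject. Separately, a Day 3 blood finding follows five uses since the last safety sample, so charging it to one product is a convention that the data cannot support.

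Only the by-product tabulation of AEs arising from Day 3 laboratory findings is affected. Laboratory summaries by day are untouched, and no PK or PD result changes. The documents give no expected number of such AEs, so the count at risk cannot be stated; it may be small.

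The urine conclusion rests on reading the timing from Table 8, whose merged rows ran together in the text available, so it should be checked against the original layout. The empty brackets in 12.7 may be a lost cross-reference and are not counted as an error.

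**What to change.** Reconcile Protocol 12.7, Table 8 and SAP 8.6 before database lock.

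1. In 12.7, correct the timing statement so that it separates the morning blood from the Table 8 urine slot.
2. Replace the previous-day rule by one of two options, and put it in SAP 8.6 and in the list of changes in SAP section 9:
   - report Day 3 laboratory AEs overall, with a listing of every product used since the Day -1 sample; or
   - state separate rules for blood and urine consistent with SAP 8.6, including what applies when the onset time is missing.
3. In SAP 8.7, state that scheduled Day 3 blood values reflect the product test and periods 1 to 4 only.

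The first option suits the sampling better, because one Day 3 sample cannot distinguish among the products used before it. Its cost is that Day 3 laboratory AEs have no single-product row. The second keeps those rows, but they should be labelled as a convention. Either way the cost is a short SAP paragraph and a clarification of 12.7. No sampling time needs to change.
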